**Table 16: BEST Items Contributing to BEST Score Calculation** 

Bro	eathlessness	Fatigue		
0	None or rarely	0	I do not feel tired	
1	Breathless when hurrying or walking up	1	I feel a little tired	
	a hill			
2	Have to walk slowly on level ground or	2	I feel tired but can still do the things I	
	stop for breath after a few minutes on		would like to do	
	level ground			
3	Can walk less than 100m or a few	3	Tiredness is stopping me from doing	
	minutes on level ground before having		things I want to do	
	to stop			
4	Breathless when washing or dressing	4	I am so tired I am unable to carry my	
			usual daily activities	
Sp	utum Volume	Sputum Color		
0	No sputum	0	No sputum	
1	Less than a teaspoon	1	White	
2	Teaspoon to an egg-cup	2	Yellow	
3	Egg-cup to a cup	3	Green	
4	More than a cup	4	Dark Green	
5		5	Blood stained	
Co	Cough		ld and Flu Symptoms	
0	None	0	None	
1	Mild	1	Sore throat, sore muscle, or runny nose	
2	Moderate	2	Fever/high temperature	
3	Severe	3		
4	Very severe	4		
5		5	I feel like I have an infection	

CONFIDENTIAL Page 106 of 139

### APPENDIX F. EQ-5D-5L SCORING ALGORITHM

The EQ-5D-5L consists of the EQ-5D descriptive system and the EQ visual analogue scale (EQ VAS). The EQ-5D descriptive system comprises the following 5 dimensions: mobility, self-care, usual activities, pain / discomfort, and anxiety / depression. Each dimension has 5 levels: no problems, slight problems, moderate problems, severe problems, and extreme problems. The patient is asked to indicate his/her health state by ticking the box next to the most appropriate statement in each of the five dimensions. This decision results in a 1-digit number that expresses the level selected for that dimension. The digits for the five dimensions can be combined into a 5-digit number that describes the patient's health state, where a higher score corresponds to a worse health state.

The EQ VAS records the patient's self-rated health on a vertical visual analogue scale, where the endpoints are labelled 'The best health you can imagine' and 'The worst health you can imagine'. The VAS can be used as a quantitative measure of health outcome that reflect the patient's own judgement.

https://euroqol.org/wp-content/uploads/2020/12/UK crosswalk SAS.txt

[figure not shown]
A sample copy of the EQ-5D-5L can be found on the next pages.

CONFIDENTIAL Page 107 of 139

### Figure 1/UK (English) EQ-5D-5L Paper Self-Complete (sample version)

Under each heading, please tick the ONE box that best describes your health TODAY.

MOBILITY	
I have no problems in walking about	
I have slight problems in walking about	
I have moderate problems in walking about	
I have severe problems in walking about	
I am unable to walk about	
SELF-CARE	
I have no problems washing or dressing myself	
I have slight problems washing or dressing myself	
I have moderate problems washing or dressing myself	
I have severe problems washing or dressing myself	00
I am unable to wash or dress myself	
USUAL ACTIVITIES (e.g. work, study, housework, family or leisure activities)	
I have no problems doing my usual activities	
I have slight problems doing my usual activities	
I have moderate problems doing my usual activities	
I have severe problems doing my usual activities	
I am unable to do my usual activities	
PAIN / DISCOMFORT	
I have no pain or discomfort	
I have slight pain or discomfort	
I have moderate pain or discomfort	
I have severe pain or discomfort	
I have extreme pain or discomfort	
ANXIETY / DEPRESSION	
I am not anxious or depressed	
I am slightly anxious or depressed	
I am moderately anxious or depressed	
I am severely anxious or depressed	
I am extremely anxious or depressed	

© EuroQol Research Foundation. EQ-5D™ is a trade mark of the EuroQol Research Foundation

CONFIDENTIAL Page 109 of 139

# APPENDIX G. SCHEDULE OF PHARMACOKINETIC SAMPLE COLLECTION

The details of the blood PK sampling scheme are described in the table below.

Pharmacokinetic blood samples will be collected from all adult participants who participate in the PK/PD substudy and all adolescent participants enrolled in the study.

Table 17: PK sample collection schedule

Day/Week	Collection Time	Collection Window	All Adult Participants	Substudy Participants a
Day 1	0 hour (predose)	_	X	X
	0.5 hour postdose	± 10 min	_	X
	2 hours postdose	± 30 min	X (optional) b	X
	4 to 8 hours postdose	_	_	X
Week 4	0 hour (predose)	_	X	X
	2 hours postdose	± 30 min	X (optional) b	X
Week 16	0 hour (predose)	_	X	X
Week 28	0 hour (predose)	_	X	X
	0.5 hour postdose	± 10 min	-	X
	2 hours postdose	± 30 min	X (optional) b	X
	4 to 8 hours postdose	_	-	X
Week 40	0 hour (predose)	_	X	X
	2 hours postdose	± 30 min	X (optional) b	X
Week 52	0 hour (predose)		X	X

a Additional PK blood samples will be collected from all adult participants who participate in the PK/PD substudy, and PK blood samples will be collected from all adolescent participants enrolled in the study. The PK/PD substudy will include participants who are not receiving cyclic antibiotics at Baseline.

CONFIDENTIAL Page 110 of 139

b While collection of the 2-hour postdose PK sample is optional, it is valuable for PK evaluation; therefore, collection of the optional 2-hour postdose sample is highly recommended.

Note: The blood sample collected for all adult participants will be used for the substudy when substudy sample collection is scheduled at the same timepoint (no extra samples will be collected).

# APPENDIX H. SCHEDULE OF PHARMACODYNAMIC SAMPLE COLLECTION

The details of the PD sampling scheme are described in the table below.

**Table 18:** PD sample collection schedule

		All Adult Participants a	Substudy Participants b	
Day/Week	Collection Time	Sputum Sample	Blood Sample c	Sputum Sample d
Screening Visit	During Screening Visit	X	X	X
Day 1	0 hour (predose)	X	X	X
Week 4	0 hour (predose)	X	X	X
Week 16	0 hour (predose)	X	X	X
Week 28	0 hour (predose)	X	X	X
Week 40	0 hour (predose)	X	X	X
Week 52	0 hour (predose)	X	X	X
Week 56	At Follow-up visit	X	X	X

a Pharmacodynamic sputum samples will be collected from all newly enrolled adult participants as introduced with global protocol amendment 3.

CONFIDENTIAL Page 111 of 139

b The PK/PD substudy will include participants who are not receiving cyclic antibiotics at Baseline.

c PD blood samples will be collected from approximately 40 adult participants enrolled in the PK/PD substudy at select sites in the United States.

d PD sputum samples will be collected from all adult participants enrolled in the PK/PD substudy. Sputum samples will also be collected from all adolescent participants who are enrolled in the study and are able to produce a sputum sample.

Note: The sputum sample collected for all participants will be used for the substudy when substudy sample collection is scheduled at the same timepoint (no extra samples will be collected).

### APPENDIX I. TECHNICAL DETAILS FOR STATISTICAL ANALYSIS

### **Primary Endpoint: Main Analysis**

```
PROC GENMOD DATA=<dataIn> ORDER=DATA;
 CLASS usubjid trtp(REF="Placebo") region1 numpes psaecol agegr3;
 MODEL count = trtp region1 numpes psaecol agegr3
       / OFFSET=ln fup DIST=NB LINK=LOG WALD TYPE3 NOINT;
 REPEATED SUBJECT=usubjid / TYPE=UNSTR COVB;
 LSMEANS trtp /exp OM;
 ESTIMATE 'brensocatib 10 vs placebo' trt 1 0 -1 / EXP E;
 ESTIMATE 'brensocatib 25 vs placebo' trt 0 1 -1 / EXP E;
 ODS OUTPUT ESTIMATES
           CONVERGENCESTATUS =
            LSMEANS
RUN;
Where:
         participants treatment (brensocatib 25mg, brensocatib 10mg,
trtp
placebo)
region1 stratification factor: North America, Europe, Japan, and the
         Rest of the World
psaecol stratification factor: sputum sample being classified as
         positive or negative for Pseudomonas aeruginosa at screening
numpes stratification factor: number of prior PEs [<3 or \geq3] in the
         previous 12 months
agegr3 age group: adult, adolescent)
count number of observed PEs
ln fup logarithm of participants time at risk (years)
Sorting: data will be sorted by usubjid
```

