#### 3.3. Randomization

After meeting all inclusion criteria and none of the exclusion criteria, adult participants will be randomized through an interactive web response system (IWRS) in a 1:1:1 ratio to 1 of the 3 treatment groups: brensocatib 10 mg, brensocatib 25 mg, or matching placebo (approximately 540 participants per treatment arm). Randomization will be stratified based on region (North America, Europe, Japan, and the Rest of the World), sputum sample classified as positive or negative for *Pseudomonas aeruginosa* at Screening Visit, and the number of prior PEs  $(2, \text{ or } \ge 3)$  in the previous 12 months.

In order to have a representative population in the study, similar to what is described in the literature, randomization will be enforced to have approximately 30% of adult participants with 3 or more prior PEs, to have no more than 20% of participants older than 75 years of age, to have approximately no more than 20% of participants with eosinophil count in peripheral blood  $\geq$ 300/mm³ at Screening, and to have no more than 20% of participants with COPD as a comorbidity.

Approximately 40 adolescent participants will be randomized through an IWRS in a 2:2:1 ratio to 1 of 3 treatment groups: brensocatib 10 mg, brensocatib 25 mg, or matching placebo (approximately 16:16:8 participants per treatment arm, respectively). Adolescent participants will not be required to produce a sputum sample at the Screening Visit if they are unable to provide. There will be no stratification for adolescent participants. To allow inclusion of adolescent data into the statistical analysis, the stratification factor covariates will be derived as follows:

- Exacerbation frequency in last 12 months from BSI form
- Colonization status from the sputum sample collection form. This is the IHMA source information for the colonization status. If the sputum result is missing, but the BSI colonization category is present then the value comes from BSI form^1. If both IHMA source and BSI colonization category are missing, presence of Pseudomonas Aeruginosa will be considered as 'Negative' for the analysis.

CONFIDENTIAL Page 20 of 139

<sup>1 The BSI form has three outcomes for colonization status: "Not Colonized", "Chronic Colonization", and "P. Aeruginosa Colonization". For the analysis the outcomes "Chronic colonization" and "P. Aeruginosa Colonization" will identify presence of Pseudomonas Aeruginosa.

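### The SAP's example code for the primary analysis lets the data set the order of the two active arms but uses positional contrasts, so the two dose labels can be exchanged

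*SAP*

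**What the plan says.** SAP Section 8.2.1 describes the negative binomial model for the annualized rate of pulmonary exacerbations and refers to Appendix I for an example program. Under the Appendix I heading for the primary endpoint's main analysis:

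- The procedure call is "PROC GENMOD DATA=<dataIn> ORDER=DATA".
- The class statement is "CLASS usubjid trtp(REF='Placebo') region1 numpes psaecol agegr3". It names a reference level for treatment and nothing else about level order.
- The two dose comparisons are "ESTIMATE 'brensocatib 10 vs placebo' trt 1 0 -1 / EXP E" and "ESTIMATE 'brensocatib 25 vs placebo' trt 0 1 -1 / EXP E".
- The LSMEANS statement asks for exponentiated means with observed margins, but not for differences.
- The legend describes the treatment variable as "participants treatment (brensocatib 25mg, brensocatib 10mg", followed by placebo, and ends with "Sorting: data will be sorted by usubjid".

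The governing text defines the comparisons by dose name. SAP Table 3 makes H1 the 25 mg comparison and H2 the 10 mg comparison. Section 6.3 takes their raw p-values as p1 and p2, and compares the adjusted values with 0.01 as well as 0.05.

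**The concern.** The contrast coefficients refer to positions: level 1 minus level 3, and level 2 minus level 3. The labels are therefore right only if level 1 is 10 mg and level 2 is 25 mg. Nothing in the code fixes that. The order of the two active arms depends on which dose appears first in the ID-sorted file.

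Because LSMEANS requests no differences, the rate ratios against placebo and their p-values come, in this code, only from the two ESTIMATE lines. An exchange would report each dose's primary result under the other dose. It would also pair each dose's secondary hypotheses with the wrong gate, since the procedure does not allow H3, for example, to be rejected unless H1 is.

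The model is also used beyond the primary analysis: for severe exacerbations (SAP 8.3.4.1), the supplementary analyses (8.2.3, 8.2.5) and the subgroups (8.2.6). Protocol 10.4.6.5 repeats the main analysis separately in adults and in adolescents. Each subset has its own first active participant, so labels could be right in one run and exchanged in another.

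**Working it through.** The plan states no figure to reproduce. The check traces the code.

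**Level order.** The documents do not describe SAS behaviour, so two points are assumed: ORDER=DATA orders class levels by first appearance, and REF= moves placebo to the last position. Two orders are then possible.

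| First active participant by ID | Level order | Coefficients 1 0 -1 (labelled 10 mg) give | Coefficients 0 1 -1 (labelled 25 mg) give |
|---|---|---|---|
| on 10 mg | 10, 25, placebo | 10 mg vs placebo | 25 mg vs placebo |
| on 25 mg | 25, 10, placebo | 25 mg vs placebo | 10 mg vs placebo |

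**Effect name.** Both ESTIMATE lines refer to trt, while CLASS and MODEL contain trtp. The lines must be edited, and the obvious edit (trt to trtp) leaves the table above unchanged.

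**Chance of an exchange.** SAP 3.3 randomizes adults "in a 1:1:1 ratio to 1 of the 3 treatment groups" and states "Approximately 40 adolescent participants will be randomized through an IWRS in a 2:2:1 ratio" for the younger cohort. The chance that the first active participant is on 25 mg is:

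- adults: (1/3) / (1/3 + 1/3) = 1/2
- adolescents: (2/5) / (2/5 + 2/5) = 1/2

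In 20,000 simulated allocations at 1:1:1 the exchanged order occurred with frequency 0.502.

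**What an exchange looks like.** One data set was simulated with 540 per arm, placebo rate 1.2 and dispersion 1 (SAP 3.2), and assumed rate ratios of 0.79 for 10 mg and 0.70 for 25 mg. It was fitted without covariates, with the dispersion held at 1 and a robust covariance.

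| Level order | Labelled 10 vs placebo | Labelled 25 vs placebo |
|---|---|---|
| 10, 25, placebo | 0.778 (p = 0.0033) | 0.666 (p = 0.000003) |
| 25, 10, placebo | 0.666 (p = 0.000003) | 0.778 (p = 0.0033) |

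The estimates are valid in both rows. In the second they carry the wrong dose.

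**Effect on the gatekeeping.** Appendix J defines f(p,q) = 2 min(p/(1+γ1), q/(1−γ1)), with γ1 = 0.9. Assume raw p-values of 0.03 for 25 mg and 0.004 for 10 mg, with secondary p-values of at least 0.01. For every secondary q, q/0.1 is at least 0.1, so the first term of f is always the smaller.

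- Simes term: min(2 × 0.004, 0.03) = 0.008
- 25 mg: max(0.03, 0.008, 2 × 0.03/1.9 = 0.0316) = 0.0316
- 10 mg: max(0.004, 0.008, 2 × 0.004/1.9 = 0.0042) = 0.008

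With p1 and p2 exchanged, the adjusted values become 0.008 for 25 mg and 0.0316 for 10 mg. In this illustration the dose that meets 0.01 changes.

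**The case against.** The sponsor can fairly say that the code is labelled an example, that the governing text defines every comparison by dose name, and that the block cannot run as printed because of the trt/trtp mismatch and the input-dataset placeholder. A programmer must edit the very lines at issue.

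The same code also contains two checks. The E option prints the contrast coefficients, and LSMEANS gives an adjusted rate under each arm's own name, which Section 8.2.1 requires to be reported. In this log-link model the rate ratio equals the quotient of two adjusted rates, so exchanged labels would contradict the reported rates. In the simulated example the line labelled 25 mg would read 0.778, while the arm-named rates would give 0.666. Nor do the sections that reuse the model prescribe these ESTIMATE lines.

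All of this stands, and it makes the problem conditional and detectable. It does not remove it. The printed sort and order rules do not deliver the order that the printed contrasts need, and the simplest correction leaves the mismatch in place.

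A reader might infer more than the documents support:

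- **That the primary result will be mislabelled.** The order may happen to be right, and a check would reveal an exchange.
- **That only 1 of the 6 possible orders is right.** That holds only if REF= leaves placebo where it first appears, which nothing in the documents establishes.
- **That the legend, by listing 25 mg first, sets the opposite level order.** It lists the variable's values and does not state an order.

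**Conclusion.** The point holds as a defect in the example code for the primary analysis. If only the effect name is corrected, the chance that the two dose labels are exchanged is about 50%, unless the programmer checks the printed coefficients or compares the ratios with the arm-named rates. This rests on ORDER=DATA and REF= behaving as assumed, on equal allocation to the two doses, and on no other change to the code. The 50% describes uncertainty before the file is seen; for any given file the order is settled.

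The consequence would be serious, because p1 and p2 would enter the gatekeeping procedure and the 0.01 comparison under the wrong dose. The model and the hypotheses as defined in the SAP text are not in question. The change should be made before unblinding.

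**What to change.** In Appendix I, replace the two ESTIMATE statements with contrasts that name the levels, for example `LSMEANS trtp / DIFF=CONTROL('Placebo') EXP CL OM`. Use the same code wherever the model is rerun: severe exacerbations, supplementary analyses, subgroups, and the separate adult and adolescent analyses.

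If a numeric treatment variable is preferred, keep the coding already used in the appendix for the Cox model and the time-to-first-exacerbation and FEV1 tipping-point code (1 = 25 mg, 2 = 10 mg, 3 = placebo). Set ORDER=INTERNAL and match the coefficients to it: 1 0 -1 for 25 mg and 0 1 -1 for 10 mg. Do not introduce the opposite coding for the primary analysis, since that would contradict the rest of the appendix.

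The cost is a few lines of appendix code. No estimand, model, alpha or data collection changes.

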# Primary Endpoint: Annualized Rate of Pulmonary Exacerbations—Tipping Point (Sensitivity Analysis)

Participants may discontinue from the study prior to the end of the 52 weeks treatment period, so that the number of PEs after discontinuation is unknown. Table 19 splits the number of events and participants time at risk into two periods, the observed period (Period 1), and the unknown period (Period 2). According to Section 6.7.1 a participant will not be at risk in the days from the start to the end of a PE. Therefore, the sum of periods T1 and T2 might be smaller than the protocol specified treatment period of 52 weeks.

Table 19: Differentiation of Events and Duration for Participants with missing Followup Time

Period:	Period 1	Period 2	Total (52 weeks)
Status:	Patient is on-study	Patient is off study	
Status.	(PEs are observed)	(PEs not observed)	

CONFIDENTIAL Page 112 of 139

Duration (years) followed:	T1	T2	T = T1 + T2
Number of PEs within the period:	$Y_1, Y_{obs}$	$Y_2, Y_{mis}$	Y = Y1 + Y2

T1 and Y1 are known, T2 and Y2 are unknown. T will be set to 1 for participants who discontinue from the study early..

T1>0, T2\ge 0. If T2=0, then Y2=0 and there is no missing data for the corresponding participant.

$$T2 = 1 - T1$$

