### 6.7. Definitions and Derivations of Efficacy Variables

### 6.7.1. Pulmonary Exacerbations

Only exacerbation events that meet the protocol definition of PE diagnosis confirmed by an independent adjudication committee will be included into the analysis (refer to Section 10.4.6.1.1 of the CSP for further details and the Clinical Endpoint Committee [CEC] Charter).

The calculation of the time at risk as well the inclusion of data into the analysis depends on the underlying Estimand. Refer to Table 5 for further details. In general, participants' time at risk will be the time on study excluding the time during exacerbations.

Table 5: PEs to be included into the analysis and time at risk based on Estimand

Estimand	PEs included in	
Name	the analysis	Time at risk
On-Study	All observed PEs	Date of Week 52 visit / early study
(Primary)	up to Week 52 who	discontinuation  – date of randomization + 1 minus
	meet the protocol	the sum of number of days the participant
	defined criteria of	experiences exacerbation events that meet the
	PE diagnosis	protocol definition of PE diagnosis (end date of the
		PE – start date of the $PE$ + 1). Refer to
		Section 6.7.1.1 for further instructions in case of
		combined PEs.
On-Treatment	All observed PEs	Date of last IP intake / date of first ICE onset –
and On-IP	up to end of IP /	date of first IP intake + 1 minus the sum of number
(Supplementary)	first ICE onset who	of days the participant experiences exacerbation
	meet the protocol	events that meet the protocol definition of PE
	defined criteria of	diagnosis prior to the first ICE (end date of the PE
	PE diagnosis	– start date of the PE + 1). Refer to Section 6.7.1.1
		for further instructions in case of combined PEs.

Rules defined above will not be applied to the analysis of PEs as AEs, e.g., not fulfilling protocol-defined criteria (see Section 7.1 of the CSP).

If a PE is ongoing at EOS, the PE end date will be EOS date, given query for resolution failed. If the PE end date is longer / after the EOS date, then the PE end date will be set to the

CONFIDENTIAL Page 38 of 139

-

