### 8.2.2. Sensitivity Analyses – Tipping Point

If there are study participants who discontinue randomized IP early and decline to remain in the study, ascertainment of data will be incomplete, and a true Treatment Policy/ITT analysis cannot be achieved. A "missing at random" (MAR) assumption for the missing data is made implicitly for the On-Study Estimand.

The main analysis using the negative binomial model is unbiased under the MAR assumption for the missing data. However, in some instances, the fact that data are missing may be directly related to the unobserved values, i.e., missing not at random (MNAR). Therefore, robustness of the main analysis to departures from the MAR assumption will be assessed using tipping-point analyses. Due to the inherent difficulties in identifying the missing data mechanism in practice, all missing data will be assumed MNAR, and the tipping point penalties will be applied accordingly.

As the first step, multiple imputations (MI) of missing PE data under the observed data model (MAR assumption) will be implemented using negative binomial model, which models the distribution of a response Y, e.g., the number of PE events, as the joint distribution of the observed responses  $Y_{obs}$  and a distribution of the missing responses  $Y_{mis}$  after discontinuation from the study. Missing post withdrawal PEs will be imputed with the predicted PE values from the model, per treatment and strata, for the time remaining after study discontinuation prior to Week 52. Refer to Figure 2 as a visualization of the different periods of a participant's participation who discontinued early from study.

Figure 2: Sensitivity Analysis: Period of Discontinued Participants

CONFIDENTIAL Page 53 of 139

For a given participant, the conditional distribution  $Y_{mis}|Y_{obs}$  is a function of the observed events  $y_1$ , the estimated dispersion, the estimated PE rate in period 1 (which is the same as obtained in the primary analysis) and the model covariates. The imputed count of PEs will be combined with the observed PE count. The process of imputing missing PE data will be repeated multiple times to create 100 separate datasets.

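### The primary tipping-point analysis sets the unobserved period to 1 minus time at risk, so exacerbation days already observed before withdrawal are counted as missing follow-up; the effect is small and slightly conservative

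*SAP*

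**What the plan says.** SAP 6.7.1 defines exposure for the primary endpoint: "In general, participants' time at risk will be the time on study excluding the time during exacerbations". The Appendix I text for the tipping-point analysis builds on that definition. It says that "Table 19 splits the number of events and participants time at risk into two periods", one observed and one unobserved. It repeats that "a participant will not be at risk in the days from the start to the end of a PE", and it concludes that "the sum of periods T1 and T2 might be smaller than the protocol specified treatment period of 52 weeks".

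Below Table 19 the rule changes: "T will be set to 1 for participants who discontinue from the study early", and T2 is 1 minus T1. Table 19 labels the second period as time when the participant has left the study and PEs are not observed.

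SAP 8.2.2, which Appendix I implements, says missing PEs are imputed "for the time remaining after study discontinuation prior to Week 52". Appendix I also gives simulated PEs a length of zero, and it applies the delta multipliers to the expected count in the second period. SAP 8.3.4.2 reuses the approach for severe PEs, with death from any cause counted as a severe PE.

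**The concern.** Two statements in the same part of the appendix cannot both hold. If T1 excludes PE days, T1 + T2 should usually fall short of a full year for someone who had PEs before withdrawing. Setting T to 1 forces the sum to a full year for every early discontinuer, and the difference goes into T2. Days observed on study as not at risk are then treated as unobserved time at risk.

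Three things follow:

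- The imputed period is longer than the one SAP 8.2.2 describes. The excess is largest for frequent exacerbators and, relative to the time left, for late withdrawals.
- The delta penalty acts on days that were never missing.
- Two programmers, one following SAP 8.2.2 and one following Appendix I, would build different imputed datasets for the analysis that tests the primary result against informative withdrawal.

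**Working it through.** **Inputs from the documents**

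- Placebo rate 1.2 per year, dispersion c = 1, rate ratio 0.70, hence 1.2 × 0.70 = 0.84 for brensocatib; 540 adults per arm (Protocol 10.1, SAP 3.2).
- Time at risk = time on study minus PE days (SAP 6.7.1, Table 5).
- One year = 365.25 days (SAP 6.4.7). Scheduled Week 52 is Day 364, i.e. randomization + 363 days (footnote to SAP Table 5).
- The imputed count given Y1 has mean (1/c + Y1) × ψ2/(1/c + ψ1), where ψ1 and ψ2 are rate × T1 and rate × T2 (Appendix I).

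**Assumed, because the documents do not give them:** PE length (7 to 28 days), timing of withdrawal, and dropout of 10 to 20%.

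**The plan's own figures.** For x = 0.3, SAP 8.2.2 gives deltas from 0.7 to 1.9 in steps of 0.15. These reproduce: 1 − 0.3 = 0.7, 1 + 3 × 0.3 = 1.9, 0.5 × 0.3 = 0.15. The rate inputs also reproduce the Protocol's 90% power per comparison: SE = √((1/1.2 + 1/0.84 + 2)/540) = 0.0863, and 0.3567/0.0863 − 2.807 = 1.325, i.e. 90.7%.

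**Step 1: the excess.** Let w be the study day of discontinuation and D the PE days up to then.

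- T1 = (w − D)/365.25
- T2 by Appendix I = 1 − T1 = (365.25 − w + D)/365.25
- Time left to Week 52 = (364 − w)/365.25
- Excess = D + 1.25 days

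**Step 2: single cases, placebo rate.**

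- Day 182 after two 14-day PEs: T1 = 154 days and T2 = 211.25 days, against 182 days left. The excess is 28 + 1.25 = 29.25 days. Expected imputed PEs are 3 × 1.2 × (211.25/365.25)/(1 + 1.2 × 154/365.25) = 1.38, against 1.19 with 182 days.
- An extreme case, Day 350 after three PEs totalling 60 days: T1 = 290 days and T2 = 75.25 days, against 14 left. Expected imputed PEs are 4 × 1.2 × (75.25/365.25)/(1 + 1.2 × 290/365.25) = 0.506, against 0.094.

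**Step 3: averages.** These come from simulated withdrawals, uniform over Days 30 to 364, with events arising only while at risk.

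| Assumed PE length | Excess imputed PEs, placebo | Excess imputed PEs, brensocatib |
|---|---|---|
| 10 days | about 8% | about 6% |
| 15 days | about 11% | about 8% |
| 20 days | about 13% | about 10% |

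The 1.25 days account for about 0.75 percentage points of each figure: mean time left is (364 − 30)/2 = 167 days, and 1.25/167 = 0.75%.

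**Step 4: both deltas at 1.** Since Y1 has mean ψ1, the imputed count has mean (1 + ψ1) × ψ2/(1 + ψ1) = ψ2 = rate × T2. The completed data are analysed with offset log(T1 + T2), so the expected rate is rate × (T1 + T2)/(T1 + T2), whatever T2 is. The rate ratio is 0.84/1.2 = 0.700 under either rule. A simulation with 300,000 participants per arm agreed to within about 0.002 under both.

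**Step 5: penalised cells.** Expected rate per arm = [(1 − q) × rate × R + q × (rate × T1 + δ × rate × T2)]/[(1 − q) × R + q × (T1 + T2)]. Here q is the dropout fraction, R is a completer's years at risk, and withdrawal is at Day 182. With 14-day PEs, q = 0.20, δ = 0.7 in placebo and 1.9 in brensocatib:

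- Appendix I rule: placebo 1.11695/0.96221 = 1.1608; brensocatib 0.89502/0.97239 = 0.9204; ratio 0.793.
- T2 as time left: placebo 1.11269/0.95714 = 1.1625; brensocatib 0.88897/0.96860 = 0.9178; ratio 0.790 (0.7895 to four places).

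Over PE lengths of 7 to 28 days, dropout of 10 and 20%, and delta pairs (placebo/brensocatib) of 1/1.3, 0.7/1.3 and 0.7/1.9, the Appendix I ratio was higher by 0.0002 to 0.0063. The largest difference was 0.7986 against 0.7923, with 28-day PEs, 20% dropout and deltas 0.7/1.9.

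**The case against.** The strongest defence is that the endpoint is a rate. Extra imputed events arrive with matching extra exposure, so counting events alone exaggerates the problem. This stands. It disposes of an inference a reader might draw, that the cell with both deltas at 1 no longer represents the primary analysis: Step 4 shows the expected ratio is the same under either rule. It also means the larger percentage excess in placebo does not by itself bias the comparison under missing at random.

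A second defence is that T = 1 is a deliberate one-year at-risk horizon, in keeping with zero-length simulated PEs. Zero length explains why PE days inside the second period are ignored. It does not explain moving first-period PE days into the second, and it conflicts with the appendix's own remark that T1 + T2 may fall below 52 weeks. It is true that some asymmetry would remain after correction, since imputed time would still contain no PE days.

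Third, the row label in Table 19 speaks of years followed, so T1 might be meant as calendar time. The surrounding text says time at risk. A calendar T1 in ψ1 would also not match the at-risk offset with which the coefficients were estimated. Either way the text needs correcting.

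Finally, SAP 6.2 runs this analysis only if the main result is significant. The primary estimate, p-value and multiplicity procedure are untouched. That is correct and limits the importance of the point.

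**Conclusion.** The rule is wrong as written and inconsistent with SAP 8.2.2, but minor. The excess of D + 1.25 days follows from the SAP's own definitions and needs no assumption. The average excess in imputed PEs (about 8 to 13% in placebo, 6 to 10% in brensocatib) depends on assumed PE lengths and withdrawal timing. That it is larger in placebo is not stated in the documents; it follows from the design rates if PE length and withdrawal timing are similar between arms.

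A reader might infer that the located tipping point is wrong, or that the rule favours brensocatib. The figures support neither. In the cells examined, all of which penalise brensocatib, the rate ratio shifts by at most about 0.006 and toward 1. Significance would therefore be lost slightly sooner, which is conservative. The tipping point can move slightly. No actual tipping point was computed, since that needs trial data.

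**What to change.** In Appendix I, replace the rule that sets T to 1 and the formula for T2 with the following:

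- For participants who discontinue the study early, T2 = max(0, 364 − study day of discontinuation)/365.25, consistent with the Week 52 date in the footnote to SAP Table 5.
- For all others, T2 = 0. Read literally, the present formula gives a Day-364 completer with no PEs T2 = 1.25/365.25 = 0.003, so the restriction should be explicit.
- T = T1 + T2, with log(T) as the offset in the imputed datasets.

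Apply the same rule to the severe-PE sensitivity analysis in SAP 8.3.4.2. The cost is about two lines of SAP text and the matching code; the primary analysis does not change.
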